1.6. OVERALL RISK AND BENEFIT ASSESSMENT

Potential Risks Based On Nonclinical Safety Data with GS-9973

Spleen tyrosine kinase deficiency and SYK-deficient bone marrow in rodents have been associated with hemorrhage. In an ex vivo platelet function assay, GS-9973 showed no biologically relevant inhibition or activation of platelets at concentrations up to 12.3 μ M. No evidence of altered coagulation parameters was noted at any dose level in the GS-9973 nonclinical studies.

The target organ(s) of toxicity identified in rats was the duodenum, and in rabbits and dogs were predominantly the gastrointestinal tract and lymphoid organs. No target organs were identified in the cynomolgus monkey. In rats treated with 500 mg/kg/day ENTO for 4 weeks, slight villus alteration in the duodenum was noted; this finding was not observed following administration of up to 100 mg/kg/day to rats for 26 weeks. In rabbits and dogs, the predominant organs affected were the GI tract and lymphoid tissues including spleen, lymph nodes, and/or the thymus. Oral administration of GS-9973 to rats for up to 26 weeks or cynomolgus monkeys for up to 39 weeks showed no evidence of GI toxicity or lymphoid changes at exposures which overlapped with or exceeded those in dogs. Clinical assessments will monitor for signs and symptoms of infection, hemorrhage, GI distress, and changes in clinical pathology parameters (changes in hemoglobin, neutrophils, lymphocytes, liver enzymes, and total and indirect bilirubin) that could occur after GS-9973 administration. Because evidence of lymphoid tissue depletion was noted in rabbits and dogs at high doses, clinical assessments will also include monitoring for signs and symptoms of infection.

Coadministration of ENTO with vincristine (VCR) did not exacerbate VCR-related hematological toxicity in male rats. Addition of GS-9973 to low dose VCR resulted in a mild slowing of caudal nerve conduction velocity compared with low dose VCR; no contributive effects of GS-9973 to nerve conduction velocity at high dose VCR were observed. The effect may be mitigated by the high plasma protein binding of ENTO (> 97%).

Administration of ENTO to pregnant female rats and rabbits resulted in dose-dependent developmental findings. The study will exclude females who are pregnant or breastfeeding, and only include female subjects of child bearing potential who are willing to use a protocol-recommended method of contraception from the screening visit throughout the study and to 30 days from the last dose of ENTO. For male subjects having intercourse with females of childbearing potential, must be willing to abstain from heterosexual intercourse or use a protocol-recommended method of contraception from the start of ENTO throughout the study treatment period and for 90 days following the last dose of ENTO.

Also, male subjects should refrain from sperm donation from the start of the ENTO throughout the study treatment period and for 90 days from the last dose of ENTO.

Potential Risks Based On Clinical Safety Data with Entospletinib (ENTO [GS-9973])

As of March 2017, 18 clinical studies have been conducted in which 470 healthy subjects (including16 subjects with hepatic impairment), 464 subjects with hematologic malignancies, 7 subjects with cGVHD, and 7 subjects with RA have participated. Of these subjects, 948 received ENTO and 26 received placebo. Overall, ENTO was generally well tolerated when administered as a single dose or as multiple doses. Treatment emergent AEs commonly reported across the studies involving healthy volunteer subjects include headache, somnolence, and GI symptoms (nausea and abdominal pain), all of which were mild and reversible.

Increased transaminases levels were noted in some subjects which is reversible.

ENTO is an inhibitor of UGT1A1 and may transiently inhibit UGT1A1 activity in vivo at the expected clinical concentrations. Administrations of drugs such as ENTO that inhibit UGT1A1 are expected to increase total bilirubin due to decreased conjugation rather than liver dysfunction. The elevations in indirect bilirubin observed in clinical trials with ENTO were generally self-limited and did not result in discontinuation of ENTO. In the absence of symptoms or other hepatic laboratory abnormalities, ENTO dose modification is not required for elevated indirect bilirubin levels.

The bis-MSA spray-dried dispersion (SDD) formulation will be used in this study and was chosen because it had less interaction with acid reducing agents. Administration of the bis-MSA formulation in studies GS-US-339-0111 and GS-US-245-1222, demonstrated that the change in ENTO exposure upon coadministration with omeprazole was less than the reduction in exposure observed in Study GS-US-245-0106 using the original formulation. The new formulation did not completely annul the DDI effect of a coadministered PPI agent, however the interaction of ENTO new formulation with an H2 receptor antagonist (H2RA) (eg famotidine) is not considered clinically meaningful.

In study GS-US-245-1222, the administration of food with the bis-MSA formulation of ENTO resulted in a reduction in ENTO exposure compared to fasted conditions. Due to this, ENTO should be taken under fasted conditions, as described in the administration instructions in this protocol.

Peripheral neuropathy has been reported with the use of vincristine. Subjects that have current or ongoing neuropathy (sensory or motor) Grade > 1 or any history of Grade \geq 3 neuropathy with prior VCR or chemotherapy exposure are excluded from the study.

Based on the clinical experience with ENTO and VCR administered as single agents, and the absence of notable additive effects with the combination in nonclinical studies, ENTO alone or in combination with VCR demonstrates an acceptable benefit/risk profile for the proposed treatment of hematological malignancies in adults.

The available nonclinical and clinical data support the evaluation of ENTO in eligible subjects with relapsed or refractory ALL.

Refer to the IB for complete details of the compound including completed and ongoing preclinical and clinical studies including summary safety and response data.

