Abbreviations: ULN=upper limit of normal, β-HCG=beta human chorionic gonadotropin, DNA=deoxyribonucleic acid, HBc antibody=anti-hepatitis B core antibody, HBsAg=hepatitis B surface antigen, HBV=hepatitis B virus, HCV=hepatitis C virus, HIV=human immunodeficiency virus, Ig=immunoglobulin, PCR=polymerase chain reaction, RNA=ribonucleic acid.

- 6) Discontinuation of all therapy (including radiotherapy, chemotherapy, tyrosine-kinase inhibitors [TKIs], immunotherapy, or investigational therapy) for the treatment of cancer as follows:
 - a) At least 1 week or 5 half-lives (whichever is longer) from the last dose of prior anti-cancer therapy and the initiation of study therapy
 - b) Exceptions or modifications to the above are as follows:

Medications that are typically part of a maintenance therapy for ALL, such as glucocorticoids or mercaptopurine, may be administered up to 3 days prior to the first dose, except vinca alkaloids which must be discontinued at least 14 Days prior to the start of study treatment. TKIs are not permitted to be continued at screening (eg, Gleevec). Subjects may receive hydroxyurea or apheresis if indicated for rapidly rising white blood cell count

- c) CNS prophylaxis up to at least one week prior to first dose of GS-9973
- d) For biologics (eg, monoclonal antibodies), washout period of 1 month beyond the recommended dosing interval and at least 4 weeks or 5 half-lives (whichever is shorter) since the last dose
- e) If prior stem cell transplant, subject must be at least 100 days from stem cell infusion and off all systemic anti-graft versus host disease (GVHD) medications

- f) If prior donor lymphocyte infusion (DLI), subject must be at least 4 weeks from DLI and off all systemic anti-graft versus host disease (GVHD) medications and have no evidence of any infection
- g) If prior Chimeric Antigen Receptor (CAR) T-Cell Therapy, subject must be at least 4 weeks from CART infusion
- All acute toxic effects of any prior antitumor therapy must be resolved to Grade ≤ 1 before enrollment, with the exception of alopecia (any grade permitted), or bone marrow parameters (any grades permitted)

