- 8) For female subjects of childbearing potential, willingness to abstain from heterosexual intercourse or use a protocol recommended method of contraception from the screening visit (Visit 1) throughout the study treatment period and to 30 days from the last dose of GS-9973. A negative serum pregnancy test is required for female subjects at screening. Lactating females must agree to discontinue nursing before GS-9973 is administered. See Appendix 5
- 9) For male subjects having intercourse with females of childbearing potential, willingness to abstain from heterosexual intercourse or use a protocol-recommended method of contraception from the start of GS-9973 throughout the study treatment period and for 90 days following the last dose of GS-9973. Also, male subjects should refrain from sperm donation from the start of the GS-9973 throughout the study treatment period and for 3 months following the last dose of GS-9973. See Appendix 5.
- 10) In the judgment of the investigator, participation in the protocol offers an acceptable benefit-to-risk ratio when considering current disease status, medical condition, and the potential benefits and risks of alternative treatments for the subject's ALL
- 11) Willingness to comply with scheduled visits, drug administration plan, imaging studies, laboratory tests, other study procedures, and study restrictions
 Note: Psychological, social, familial, or geographical factors that might preclude adequate study participation should be considered
- 12) Have the ability to understand and sign a written informed consent form, which must be obtained prior to initiation of study procedures

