4.3. Exclusion Criteria

Subjects who meet *any* of the following exclusion criteria are not to be enrolled in this study.

- 1) Diagnosis of mature B-cell ALL (Burkitt's leukemia), or lymphoid blast crisis of chronic myelogenous leukemia (CML)
- 2) A life threatening illness, medical condition or organ system dysfunction which, in the investigator's opinion, could compromise the subject's safety or interfere with the absorption or metabolism of GS-9973

3) Active or symptomatic central nervous system (CNS) disease

For study purposes a subject will NOT be considered as having active CNS disease if the subject has documentation of prior CNS disease and has received treatment (IT or radiation) and are:

- a) asymptomatic for the last 28 days prior to screening, and
- b) has documented at least 2 negative cerebrospinal fluid (CSF) cytology (which must include 1 lumbar puncture [LP] within the study screening window)
- 4) Uncontrolled intercurrent illness including, but not limited to, unstable angina pectoris or psychiatric illness/social situations that would limit compliance with study requirements. Subjects with active infection are permitted to enroll provided that the infection is documented to be under control and after discussion with study Sponsor
- 5) History of myelodysplastic syndrome or solid organ transplantation
- 6) History of a non-lymphoid malignancy except for the following:

adequately treated local basal cell or squamous cell carcinoma of the skin, cervical carcinoma in situ, superficial bladder cancer, asymptomatic prostate cancer without known metastatic disease and with no requirement for therapy or requiring only hormonal therapy and with normal prostate specific antigen for > 1 year prior to the start of GS-9973, or any other cancer that has been in complete remission without treatment for ≥ 5 years prior to enrollment

- 7) Known hypersensitivity or intolerance to any of the active substances or excipients in the formulations for GS-9973
- 8) Evidence of uncontrolled systemic bacterial, fungal, or viral infection at the start of GS-9973 *Note: Subjects with localized fungal infections of skin or nails are eligible. Subjects may be receiving prophylactic antiviral, antifungal, or antibacterial regimens (eg, anti-pneumocystis prophylaxis at the discretion of the investigator per institutional guidelines. If azoles are used for antifungal prophylaxis, subjects must be monitored for possible DDI with VCR)*

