- 9) Ongoing drug-induced liver injury, chronic active hepatitis C (HCV), chronic active hepatitis B (HBV), HIV, alcoholic liver disease, non-alcoholic steatohepatitis, primary biliary cirrhosis, extrahepatic obstruction caused by cholelithiasis, cirrhosis of the liver, or portal hypertension
- 10) Prior allogeneic bone marrow progenitor cell transplant within 100 days or on active systemic immunosuppression for graft versus host disease (GVHD) treatment or prophylaxis within 28 days prior to enrollment
- 11) Active (symptomatic or requiring current medical treatment within 28 days prior to the start of study treatment) for GVHD

- 12) Ongoing immunosuppressive therapy other than corticosteroids (corticosteroids being used for GVHD treatment are not permitted)
 Note: Subjects may use topical, enteric, inhaled, or systemic corticosteroids as therapy for manifestations of comorbid conditions
- 13) Current therapy with proton pump inhibitors (PPI) must be avoided (as there is the potential to interfere with GS-9973 absorption).*Note:* H2 blockers and antacids will be allowed for the use during the study
- 14) Pregnancy or breastfeeding
- 15) Ongoing active pneumonitis
- 16) Concurrent participation in an investigational drug trial with therapeutic intent defined as prior study therapy within 28 days prior to start of GS-9973 administration
- 17) Ongoing or recent treatment with an excluded medication, as defined in Section 5.3, Excluded Medication

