6.3.2. Biomarker Samples for Optional Future Research

6.4. Pretreatment Assessments

6.4.1. Screening Visit

Subjects will be screened within 28 days of their first administration of study treatment to determine eligibility for participation in the study. The following will be performed and documented at screening:

- Obtain written informed consent
- Obtain medical history
- Obtain smoking status
- Complete physical examination including, vital signs, body weight, and height
- Obtain blood samples
- Bone marrow aspirate/biopsy (if not done within 28 days of the first dose of GS-9973)
- CT scan or PET-CT of affected site/s for subjects with EMD only and without measureable BM involvement
- Record any serious adverse events and all adverse events related to protocol mandated procedures occurring after signing of the consent form

Subjects meeting all of the inclusion criteria and none of the exclusion criteria will return to the clinic within 28 days of screening for enrollment into the study.

From the time of obtaining informed consent through the first administration of study drug (GS-9973), record all serious adverse events (SAEs), as well as any adverse events related to protocol-mandated procedures on the adverse events case report form (CRF/eCRF). All other untoward medical occurrences observed during the screening period, including exacerbation or changes in medical history are to be captured on the medical history CRF/eCRF. See Section 7.6 Adverse Events and Toxicity Management for additional details.

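### Section 1.6 of the protocol excludes subjects with past Grade 3 or worse neuropathy on vincristine or chemotherapy, but no listed eligibility criterion does so

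*Protocol*

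**What the plan says.** Protocol Section 1.6 gives a two-part neuropathy exclusion straight after naming peripheral neuropathy as a known effect of vincristine. One part bars ongoing sensory or motor neuropathy above Grade 1. The other bars a past event of Grade 3 or worse: subjects with such "neuropathy with prior VCR or chemotherapy exposure are excluded from the study". The statement is categorical and leaves nothing to the investigator.

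Section 6.4.1 sets the route into the trial: "Subjects meeting all of the inclusion criteria and none of the exclusion criteria will return to the clinic" for enrolment. The lists it refers to are the 12 inclusion criteria of Section 4.2 and the 17 exclusion criteria of Section 4.3, repeated in the synopsis.

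The listed criteria that come nearest to the subject are:

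- Inclusion 7: "All acute toxic effects of any prior antitumor therapy must be resolved to Grade ≤ 1 before enrollment", with exceptions only for alopecia and bone marrow parameters.
- Inclusion 6b: a washout for maintenance drugs, "except vinca alkaloids which must be discontinued at least 14 Days prior to the start of study treatment".
- Inclusion 10: "In the judgment of the investigator, participation in the protocol offers an acceptable benefit-to-risk ratio".
- Exclusion 2: "A life threatening illness, medical condition or organ system dysfunction which" the investigator thinks could endanger the subject or disturb handling of GS-9973.

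SAP Section 4.3 plans a by-subject listing of enrolled subjects who failed at least one inclusion or exclusion criterion. SAP Section 5.3 plans a by-subject listing of medical history and says that general medical history will not be coded.

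**The concern.** The protocol states the same safety rule in two places with different content. A site working from the lists could enrol a subject whom Section 1.6 says is barred. The situation is foreseeable: all subjects are previously treated, and inclusion 6b anticipates recent vinca alkaloid use. The trial then gives vincristine at up to 2 mg per dose, with no dose modification during Lead-in or Cycle 1 (Section 3.5.2.1).

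Safety is the primary objective. A reader of the report would reasonably take Section 1.6 as a description of who could be treated, and would read the neuropathy adverse events in that light. The listed criteria do not support that description, and the planned eligibility-deviation listing would not reveal a departure from it, because that listing is tied to the numbered criteria.

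**Working it through.** No figure needs reproducing, so the check is a comparison of texts.

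**Step 1. Search the lists.** Criteria that name neuropathy: 0 of 12 inclusion and 0 of 17 exclusion, in Sections 4.2 and 4.3 and again in the synopsis. The exclusions run from 1 to 17 with no gap and no redaction mark, so the absence is not an artefact of the public copy. Elsewhere in the protocol, neuropathy appears as a listed vincristine side effect (Section 1.5.1) and in the vincristine dose-modification table of Appendix 3, which applies after Cycle 1. Neither is an eligibility rule, and the SAP adds none.

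**Step 2. Pass a test subject through the lists.** Take a subject who had Grade 3 neuropathy on earlier vincristine, now Grade 1 or absent, with the last vinca dose more than 14 days ago.

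| Criterion | Result for this subject |
|---|---|
| Inclusion 4 and 5 (laboratory values, no known cardiac dysfunction) | No neurological requirement; passes |
| Inclusion 6b (vinca washout) | Concerns time since dosing, not past toxicity; passes |
| Inclusion 7 (toxicity resolved to Grade 1 or less) | Concerns present grade only; passes |
| Exclusion 7 (intolerance) | Limited to GS-9973; does not apply |
| Inclusion 10, exclusion 2 | Investigator's opinion; may or may not bar |

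The subject passes every criterion that does not depend on opinion. Section 1.6 bars the same subject outright.

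**Step 3. Treat the two limbs separately.** For ongoing neuropathy above Grade 1, inclusion 7 uses the same threshold and does not exempt neuropathy. What remains is neuropathy not regarded as an acute effect of antitumour therapy, which is a narrow gap. For past Grade 3 or worse neuropathy there is no counterpart.

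**Step 4. Compare with another Section 1.6 eligibility statement.** "The study will exclude females who are pregnant or breastfeeding" reappears as exclusion 14, "Pregnancy or breastfeeding". The contraception and sperm-donation statements reappear in inclusions 8 and 9. This makes an omission from the lists plausible, though it does not prove that the lists, rather than Section 1.6, are in error.

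**Step 5. Follow the subject into the SAP.** The eligibility listing of SAP Section 4.3 is triggered by failing a numbered criterion. The test subject fails none, so that listing would not show the subject. The history could appear only in the uncoded medical-history listing of SAP Section 5.3.

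**The case against.** The strongest reply is that the two texts can both be obeyed. Section 1.6 is protocol text, Section 1.7 requires compliance with the whole protocol, and no criterion says that such a subject may enrol. This stands in part: the lists do not grant permission, and a careful site would apply Section 1.6. But Section 6.4.1 sends sites to the lists, and a rule found only in the benefit-risk narrative is easily missed.

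A second reply is that the trial protects such subjects by other means. Section 3.5.2.1 removes a subject whose Cycle 1 toxicity requires stopping any drug and counts the event as a DLT. Section 3.5.2.2 provides for holding treatment and reducing vincristine, and Appendix 3 addresses unacceptable neuropathy after Cycle 1. Section 5.2.1 points to the vincristine package insert. These provisions lower the stakes, but they act after dosing and do not decide who is enrolled.

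The third reply is timing, and it stands in full. Section 3.3 describes escalation as complete, and Section 3.3.2 says that expansion closed with no subjects enrolled. The treated subjects therefore appear to have entered under earlier amendments, whose criteria are not shown. A reader might infer that subjects with severe past neuropathy were in fact enrolled, or that DLT counts or escalation were affected. The documents support neither: they give no number of such subjects, and Section 3.3.2 reports no DLTs.

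A reader might also infer that the benefit-risk conclusion collapses without the exclusion. Section 1.6 rests that conclusion on single-agent experience and on the lack of notable additive effects in nonclinical studies, and does not cite the neuropathy exclusion as a ground for it.

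**Conclusion.** The point holds as an internal inconsistency within Amendment 5. Section 1.6 states a categorical exclusion for past Grade 3 or worse neuropathy, and 0 of 29 listed criteria (12 + 17) implements it. Only investigator discretion under inclusion 10 or exclusion 2 could keep such a subject out through the lists. The ongoing-neuropathy limb is largely covered by inclusion 7 and is not the issue.

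Severity is minor. Confidence is high about the missing criterion. Nothing can be concluded about the subjects actually treated, since neither the earlier criteria nor the subjects' neuropathy histories are in the documents. That enrolment has ended is inferred from Sections 3.3 and 3.3.2. Which of the two statements reflects the sponsor's intention is also unknown.

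**What to change.** In the protocol, add the Section 1.6 neuropathy wording as a numbered exclusion in Section 4.3 and the synopsis. If the exclusion was not intended, delete it from Section 1.6. Either is a one-line change, but with enrolment apparently over it would screen nobody new.

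The practical step is in the clinical study report. It should not repeat the Section 1.6 statement unchecked. It should say whether the exclusion was applied, and how many treated subjects had a past Grade 3 or worse neuropathy on vincristine or other chemotherapy, or that the number is unknown. The source is the medical-history listing of SAP Section 5.3, read beside neuropathy events in the adverse-event listing of SAP Section 7.1.6.1.

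The cost is a small manual review and one or two sentences of text. No new data collection is needed. Because general medical history is uncoded, someone must read the entries by hand. The documents do not say whether the grade of past events was recorded, so the answer may be unknown for some or all subjects.
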